## 2.4. Statistical Hypotheses / Statistical Analyses

The purpose of the study is to evaluate the incidence of AESI over 5 years in adults with SLE being treated with and without BENLYSTA in a real-world setting. No formal statistical hypotheses testing will be conducted since there is no pre-specified hypothesis for any of the study endpoints.

Unless otherwise specified, the following measures will be used:

- Categorical variables will be summarized as the number of subjects and percentages (%) of subjects in each category. Percentages will not include the missing category and will be calculated over the number of subjects with available (non-missing) data.
- Continuous variables will be summarized using the mean, standard deviation (SD), median, first and third quartiles (Q1, Q3), minimum (min), maximum (max).
- Computed percentages will be presented with one decimal place. Percentages equal to 100 will be presented as 100% and no percentage will be presented for zero frequencies. In case of presenting CIs for categorical/qualitative data, exact methods for deriving these intervals will be used in case of descriptive statistics.
- The 95% CI will be computed for rates to contextualize the extent of random error but will not be used for formal statistical hypothesis testing.

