
1. Incidence rate will be calculated for each exposure group as follows:
 $\text{Incidence Rate} = \frac{\sum \text{at risk subjects with at least one event}}{\sum \text{subject years at risk}} \times 100$ 
 
- Incidence rate is defined as the number of 'at-risk' subjects experiencing first event (i.e. number of new cases) during the specified follow-up period divided by total subject-years at-risk of that event for all subjects at risk.
 
- Although the categorization of study follow-up time to Benlysta (Exposed) or Non-Benlysta (Unexposed) depends on the exposure assignment strategy (see Appendix 2, Section 9.2.1 for further discussion), the follow-up time included in the subject-years at-risk calculation, for each month xx time period, starts from enrollment date and ends at the earliest of the following: 
 
o First event date
 
o Last contact date (as defined in Section 9.5.3)
 
o Month xx target date (Section 5.3)
 
o Censored date (for While on Initial Exposure strategy; see Section 9.2.1.1)
 
o Data cut-off date
 
 
Additionally, for some exposure strategies (e.g. 'As-Exposed' strategy; see Appendix 2, Section 9.2.1.2), time to treatment switch and risk windows are also considered when categorizing follow-up time into 'Exposed' and 'Unexposed' period.
 
 
- Calculation of an individual's subject-years at-risk for each exposure strategy is shown in Section 9.2.
 
- Subject-years at-risk will be calculated for each event type separately.
 
- Only the first experience of the event (i.e. new cases) or first primary diagnosis (in the case of a malignant event) which occurred during the 'at-risk' period are counted (see Section 9.2.1 for time period considered for each exposure strategy).
 
- For summary of each specific AESI category, subjects experiencing events in multiple AESI categories will be counted in more than 1 AESI category.
 
 
2. Event rate will be computed for each exposure group as follows:
 $\text{Event rate} = \frac{\sum \text{all AESI events}}{\sum \text{subject years of follow-up}} \times 100$ 
 
- Event rate is estimated for potentially recurrent events and represents the average number of events per unit time of follow-up. It is defined as the total number of events experienced by all subjects during the specified study period divided by subject-years of follow-up. The categorization of study follow-up time depends on the exposure strategy (see Appendix 2, Section 9.2.1). The subject-years of follow-up for each month xx time period takes the same definition above for the subject-years at-risk, however, follow-up does not stop at the time of first event.
 
- Additionally, for some exposure strategies (e.g. 'As-Exposed' strategy), time to treatment switch and risk windows are also considered when categorizing follow-up time into exposed and unexposed period (Section 9.2.1.2)
 
- All events experienced during the follow-up period including recurrent events are counted (see Section 9.2.1 for time period considered for each exposure strategy).
 

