

- Calculation of an individual's subject-years of follow-up for each exposure strategy is shown in Appendix 2 (Section 9.2).

 
Incidence and event rates will be calculated and reported per 100 subject-years. The 95% CI for the rate will be calculated assuming an exact Poisson distribution method [Stokes, 2012].

Model Checking & Diagnostics

• No model-based statistical analysis will be performed; hence there is no model checking and diagnostics to be conducted.

Results Presentation
Total number of events, number and % of subjects with events, total subject-years at-risk, and total subject-years of follow-up will be reported. In addition, incidence proportion (where applicable), incidence rate, event rate and their 95% CI will be presented. The mock-shell tables showing details of data displays are presented in Appendix 12.
Subgroup Analyses
This analysis may be conducted for each study cohort separately (Current Users and Treatment Initiators; Section 5.6.2) . The list of TLF Data Displays is presented in Appendix 11.
Sensitivity Analyses
This analysis will also be conducted using the 'Evaluable Sensitivity' population. Details of the planned displays are provided in Appendix 11: List of TLF Data Displays.

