#### **7.2.4. Statistical Analyses / Methods**

Endpoints listed in Section 7.2.1 will be summarised and presented as specified in Section 7.2.2. Details of the planned displays are provided in Appendix 11: List of TLF Data Displays.

Incidence and event rates of hospitalizations will be computed with 95% CI following the same approach described in Section 7.1.5.

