### 7.3.1.5. Incidence and event rate analysis

Weighted incidence rate per 100 person-years and weighted event rate per 100 person years will be presented for 'ITT' and 'While-On-Initial Exposure' treatment strategies. The 95% CI for the rates will be calculated assuming an exact Poisson distribution method.

Incidence rates will be calculated as total weighted incidence divided by total weighted subject years at risk with corresponding weighted exact Poisson CI:

$$\text{Lower} = \frac{(\text{quantile}('CHISQ', 0.025, 2 * \sum \text{weight} * \text{subject with at least one event})/2)}{\sum \text{weight} * \text{subject years at risk}}$$

$$\text{Upper} = \frac{(\text{quantile}('CHISQ', 0.975, 2 * (\sum \text{weight} * \text{subject with at least one event} + 1))/2)}{\sum \text{weight} * \text{subject years at risk}}$$

Event rates will be calculated as total weighted number of events divided by total weighted follow up time. with corresponding weighted exact Poisson CI:

$$\text{Lower} = \frac{(\text{quantile}('CHISQ', 0.025, 2 * \sum \text{weight} * \text{events}) /2)}{\sum \text{weight} * \text{subject years of follow-up}}$$

$$\text{Upper} = \frac{(\text{quantile}('CHISQ', 0.975, 2 * (\sum \text{events} + 1))/2)}{\sum \text{weight} * \text{subject years of follow-up}}$$

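### The exact Poisson interval on event rates ignores clustering of repeat events within patients, so it is too narrow for serious infections and hospitalizations when patients differ in risk

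*SAP*

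**What the plan says.** SAP section 7.1.5.1 defines two quantities for the AESI. The incidence rate counts each subject's first event and stops time at risk there. The event rate is different: "Event rate is estimated for potentially recurrent events and represents the average number of events per unit time of follow-up". Its follow-up continues past the first event, and "All events experienced during the follow-up period including recurrent events are counted".

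Both rates then receive one interval: "The 95% CI for the rate will be calculated assuming an exact Poisson distribution method". The same section adds: "No model-based statistical analysis will be performed; hence there is no model checking and diagnostics to be conducted".

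The rule reaches further in two places. For hospitalizations, section 7.2.4 says: "Incidence and event rates of hospitalizations will be computed with 95% CI following the same approach described in Section 7.1.5". For the weighted rates, section 7.3.1.5 says: "The 95% CI for the rates will be calculated assuming an exact Poisson distribution method", with chi-square limits written out for the event rate as well as the incidence rate. Section 7.3.1 names a weighted Poisson regression as the outcome model but gives no variance estimator for it.

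Neither document contains a subject-clustered or robust variance, a negative binomial model, a bootstrap or a check for overdispersion. Section 2.4 gives the purpose of the intervals: "The 95% CI will be computed for rates to contextualize the extent of random error". They are not for formal testing.

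**The concern.** The exact Poisson interval assumes that the variance of the total count equals its mean. A count of one first event per subject meets this closely enough. A count that includes recurrences meets it only if patients share one underlying rate and events arise independently. If a minority of patients has several serious infections or admissions and most have none, the total varies more than Poisson and the interval is too short.

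The protocol indicates that risk does vary. Section 1.1 describes disease activity as an independent risk factor for infection and links corticosteroids and immunosuppressants to infection. Appendix 7 lists a history of serious infection among the potential confounders.

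SAP section 7.1.2 makes the event rate a summary measure for every AESI category except mortality, and section 7.3.3 labels the weighted event rate a primary analysis. With no hypothesis tests planned, these intervals are the only planned statement of uncertainty around the event rates. If they are too short, a chance gap between the groups looks firmer than it is.

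**Working it through.** **Inputs from the protocol (section 8.2 and Table 8-1).** 2,000 and 1,000 patients, 5 years of follow-up, 10% annual drop-out. Reference rates per 100 patient-years: serious infection 5.80, opportunistic infection 0.136, malignancy excluding NMSC 0.226, NMSC 0.226, serious psychiatric events 0.410.

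**Inputs assumed.** Each patient's rate is multiplied by a gamma frailty with mean 1 and variance k. The documents give no value for k, so 0.5, 1, 2 and 4 are used. They give no hospitalization rate either; 15 to 30 per 100 patient-years is assumed.

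**Step 1: reproduce the plan's own figures.** Let L = −ln(0.9) = 0.10536 and t = min(Exp(L), 5). Then E[t] = (1 − 0.9⁵)/L = 0.40951/0.10536 = 3.887 years. This gives 7,773 and 3,887 patient-years, against 7,773 and 3,886 in the protocol. For serious infection, the half-width of the difference is 1.96 × √(0.058 × (1/7,773 + 1/3,886)) = 0.00927, or 0.93 per 100 patient-years, as stated. The setup matches the protocol's.

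**Step 2: variance inflation.** Given t, the variance of a patient's count is rt + k r²t². Summed over patients, the variance of the total relative to Poisson is

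V = 1 + k × r × E[t²]/E[t], with E[t²]/E[t] = 4.563 years.

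For serious infection, r × 4.563 = 0.058 × 4.563 = 0.265. The correct interval is √V times as wide as the Poisson one. Half-widths below are per 100 patient-years; coverage is that of the nominal 95% exact Poisson interval.

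| k | V | √V | Half-width, BENLYSTA (Poisson 0.54) | Half-width, comparison (Poisson 0.76) | Coverage |
|---|---|---|---|---|---|
| 0.5 | 1.13 | 1.06 | 0.57 | 0.81 | about 94% |
| 1 | 1.26 | 1.12 | 0.60 | 0.85 | 92–94% |
| 2 | 1.53 | 1.24 | 0.66 | 0.94 | 88–90% |
| 4 | 2.06 | 1.43 | 0.77 | 1.09 | about 84% |

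Coverage comes from 2,000 to 4,000 simulated cohorts per setting, using the SAP's chi-square limits. These values of k correspond to about 1.20, 1.26, 1.38 and 1.59 events per affected patient. With k = 0, coverage was about 95%, so counting recurrences is not in itself the fault; variation in risk between patients is. For k = 1, 2 and 4, a subject-level robust interval covered about 95%.

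**Step 3: shorter periods.** Many tables are by time period. At 12 months E[t²]/E[t] is about 0.98 years, so V for serious infection is 1.06, 1.11 and 1.23 for k = 1, 2 and 4, with coverage of about 95%, 94% and 93%.

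**Step 4: rare categories, at the most extreme k = 4 over 5 years.**
- Opportunistic infection: V = 1 + 4 × 0.00136 × 4.563 = 1.02, so √V = 1.01.
- Malignancy and NMSC: V = 1 + 4 × 0.00226 × 4.563 = 1.04, so √V = 1.02.
- Psychiatric events: V = 1 + 4 × 0.0041 × 4.563 = 1.07, so √V = 1.04.

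**Step 5: frequent events.** At an assumed 25 hospitalizations per 100 patient-years, V is 2.1, 3.3 and 5.6 for k = 1, 2 and 4, with coverage of about 83%, 71% and 60%. Across 15 to 30 per 100 patient-years, √V runs from 1.30 (15, k = 1) to 2.54 (30, k = 4).

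**The case against.** The strongest reply is that this concerns a secondary quantity. SAP section 2.2 states the primary endpoint as a comparison of incidence rates, and words the hospitalization endpoint the same way. Sections 2.4 and 5.7 rule out formal testing, and no interval for a difference or ratio of rates is specified. The planned displays show total events beside subjects with events, so a reader can see how much recurrence there is. This stands, and it limits the seriousness of the point. It does not remove it: the only stated purpose of the interval is to show random error, and for recurrent events it understates that error.

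The second reply is that the size rests on assumptions. That also stands. Neither k nor the hospitalization rate is in the documents, and the lowest coverage figures combine an assumed rate with the most extreme k over the longest follow-up. Shorter periods, and the shorter person-time of switchers under the on-exposure strategies, give less inflation.

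The third reply concerns the remedy. A robust interval for every event rate would do harm in sparse rows. Opportunistic infection in 1,000 comparison patients at 12 months has about 1,000 × 0.949 × 0.00136 = 1.3 expected events. In simulation with k = 1, some 26–28% of cohorts had none. A log-link robust interval does not exist there, and a bootstrap returns zero width. Counting those cohorts as failures, robust coverage was 69%, against 99% for exact Poisson. The remedy must therefore be selective.

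**Conclusion.** The point holds for event rates of serious infections and hospitalizations, and possibly of other infections of interest, for which no reference rate is given. It should be fixed, but it does not undermine the registry's main comparison. The direction is clear whenever patients differ in risk. The size is illustrative: for serious infection over full follow-up, intervals should be 6% to 43% wider for k from 0.5 to 4. The protocol does not say whether 5.80 counts first or all events; if it counts first events only, the all-event rate and the inflation would be higher.

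A reader might infer three stronger things that the documents do not support.
- That the primary AESI intervals are wrong. The unweighted first-event incidence rates count one event per subject and are untouched.
- That every AESI is affected. At the protocol's reference rates the effect is negligible for opportunistic infections, malignancy, NMSC and serious psychiatric events.
- That a false-positive rate is inflated. No test is planned; the consequence is overstated precision.

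Nor does this point support the exact Poisson interval on the weighted incidence rates of section 7.3.1.5. There the numerator is a sum of weights, not a Poisson count, and that is a separate question.

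**What to change.** - For event rates of serious infections, other infections of interest and hospitalizations (AESI Tables 24.x, hospitalization Tables 13.x and the matching rows of Tables 54.x), take the 95% interval from a log-link Poisson model with log person-years as offset and robust variance clustered on subject, or from a subject-level bootstrap. In Tables 54.x, the weighted Poisson regression already named in section 7.3.1 can carry the clustered variance.
- Keep the exact Poisson interval for unweighted first-event incidence rates and for sparse or zero-event rows. State in advance the event count below which a row is treated as sparse.
- Amend the statement in section 7.1.5.1 that no model-based analysis will be performed, and the cross-reference in section 7.2.4, to match.
- Add the distribution of events per subject for these endpoints, so that the extent of clustering is visible.

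The cost is SAP wording, a little more programming and wider intervals. Point estimates do not change and no new data are needed. The change should be settled before the final tables are produced.

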**7.1.5.2. Statistical Methodology Specification related to study withdrawal event**

Endpoint / Variables

 
• Study Withdrawal event
 

Endpoint Specification

1. The percentage of subjects withdrawing from the study at the time of the final analysis data cut will be calculated for each exposure group, using the Kaplan-Meier product-limit estimator for the survival probability (the probability of not withdrawing from the study), as follows:
 $\hat{S}(t) = \prod_{t_i \leq t} \left(1 - \frac{d_i}{n_i}\right)$ 
 
- <math>t_i</math> is the specific time of interest when at least one event occurred
 
- <math>d_i</math> is the number of dropout events at time <math>t_i</math>.
 
- <math>n_i</math> is the number of subjects at-risk up to time <math>t_i</math>.
 
 
2. Withdrawal rates at time <math>t</math> will be computed at time <math>t</math>, denoted as <math>\hat{F}(t)</math>:
 $\hat{F}(t) = 1 - \hat{S}(t)$ 
The probabilities of survival and study withdrawal will be expressed in percentage (%), along with 95% CI, for the following time points: 12, 24, 36, 48, 60 months. Additionally the cumulative number of withdrawals will be presented, along with percentage (calculated as cumulative number of withdrawals/N).
 
For the following time periods: 0-12, 12-24, 24-36, 36-48, 48-60 months, the number at-risk at the start of each time period, along with number of withdrawals during each time period will be presented. Percentage is calculated as <number of withdrawals during time point> / <the number at risk at the start of time period>

Model Checking & Diagnostics

 
• No model-based statistical analysis will be performed; hence there is no model checking and diagnostics to be conducted.
 

Results Presentation

The mock-shell tables showing details of data displays are presented in Appendix 12.

Subgroup Analyses

This analysis may be conducted overall and for each study cohort separately (Current Users and Treatment Initiators; Section 5.6.2) and by relevant clinical covariate listed in Section 5.6.1. The list of TLF Data Displays is presented in Appendix 11.

Sensitivity Analyses

N/A

## 7.2. Effectiveness Analyses

Overview of planned selected effectiveness measures is shown in Table 3. The analyses will be conducted using ‘Evaluable’ analysis population and by study exposure defined using the ‘Initial Exposure’ strategy (see section 9.2.1.1) and/or by strata of clinical covariates listed in Section 5.6.1. Appendix 11: List of TLF Data Displays provides details of the analyses to be conducted.

**Table 3 Overview of Planned Effectiveness Analyses**

Mock shell Endpoint	Absolute							Change from Baseline						
	Stats Analysis			Summary		Individual		Stats Analysis			Summary		Individual	
	T	F	L	T	F	F	L	T	F	L	T	F	F	L
Clinical														
SLICC/ACR Damage Index (SDI)				Y							Y			
Hospitalizations experienced	Y			Y										
Average Corticosteroid dose (mg/day)				Y							Y			
Concomitant SLE medications and corticosteroid use				Y			Y							

**NOTES:**

- T = Table, F = Figure, L = Listing, Y = Yes display type generated. Empty cell implies ‘No’ display type generated.
- Stats Analysis = display type for statistical analysis (i.e. modelling and computation of rates) of event count data.
- Summary = display type for summaries (i.e. descriptive statistics) of the observed raw data.
- Individual = display of individual subject observed raw data.

### 7.2.1. Endpoints

The effectiveness (other) endpoints assessed include:

- Organ damage as assessed by SLICC/ACR Damage Index (SDI)
  - Absolute and change from baseline for SDI composite score
  - Count of subjects with each SDI domain component
  - Count of subjects with no change in SDI, and SDI worsening (i.e. change from baseline  $\geq 0$ ) as SDI score change 0, 1, 2 and  $\geq 3$
  - Count of subjects in each permutation of baseline score and subsequent follow-up scores, to quantify how the scores change from baseline (0 to 0, 0 to 1, 0 to 2, etc) over the follow-up period
- Concomitant SLE medication and corticosteroid use

- Use of concomitant SLE medication (Yes or No)
- Use of concomitant immunosuppressants (Yes or No)
- Use of concomitant corticosteroids (Yes or No)
- If concomitant corticosteroid use is ‘Yes’:
  - Concomitant corticosteroid dose (mg/day) (Always <7.5mg/day, ≥7.5mg/day for ≤ 2 weeks or ≥7.5mg/day for > 2 weeks)
  - Absolute and change from baseline of average corticosteroids dose (mg/day)
- Hospitalization events
  - Count of events and subjects hospitalized for All-cause
  - Count of events and subjects hospitalized for SLE-related reasons

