**2.2. Study Objective(s) and Endpoint(s)**

Objectives	Endpoints
Primary	Primary
To evaluate the incidence of selected adverse events of special interest (AESI) over 5 years in adults with active autoantibody-positive systemic lupus erythematosus (SLE) who are treated with or without BENLYSTA	Comparison of incidence rates, over a 5-year period, of listed Adverse Events of Special Interest (AESI) among adult SLE subjects who are exposed or unexposed to BENLYSTA: 
 
1. Malignancies (excluding non-melanoma skin cancers)
 
2. Mortality
 
3. Opportunistic infections (serious and non-serious)*
 
4. Other infections of interest (serious and non-serious)*
 
5. Non-melanoma skin cancers (NMSC)
 
6. Serious psychiatric events
 
7. Serious infections
 

Other	Other
To evaluate selected effectiveness measures in adults with active autoantibody-positive SLE who are treated with or without BENLYSTA	
 
1. Comparison of mean change from baseline in SLICC/ACR Damage Index (SDI) score over a 5-year period in adult SLE subjects who are exposed or unexposed to BENLYSTA
 
2a. Comparison of proportions of subjects with concomitant SLE medication use, including steroids (as defined below), over a 5-year period in adult SLE subjects who are exposed or unexposed to BENLYSTA                             
Over the past six months the daily dose was either:
 
 
i. Always < 7.5 mg/day
 
ii. >= 7.5 mg/day for <= 2 weeks
 
iii. >= 7.5 mg/day for > 2 weeks
 
 
 
2b. Comparison of mean change from baseline in six-month average daily corticosteroid dose (prednisone equivalent, mg/day) assessed over 5-year period in adult SLE subjects who are exposed or unexposed to BENLYSTA
 
3. Comparison of incidence rates, over a 5-year period, of hospitalizations (as shown below) among adults SLE subjects who are exposed or unexposed to BENLYSTA:                             
 
i. All hospitalizations
 
ii. SLE-related hospitalization
 
 
 

Tertiary/Exploratory	Tertiary/Exploratory
NA	NA

\* Computation of rates will be done separately for opportunistic infections and other infections of interest (these were combined as one in the protocol)

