### 7.2.2. Summary Measure

The following measures will be used to summarize endpoints listed on Table 3 and in Section 7.2.1 above.

- Continuous endpoints such as absolute and change from baseline SDI score, absolute and change from baseline average corticosteroids dose (mg/day)
  - Summary statistics including number of observations, mean, SD, median, range (min; max) and interquartile range (Q1; Q3)
- Categorical binary, nominal and/or ordinal endpoints such as SLE medication use (immunosuppressants vs. others), use of corticosteroids (Yes or No), oral corticosteroids dose (mg/day) use (Always <7.5mg/day, ≥7.5mg/day for ≤ 2 weeks or ≥7.5mg/day for > 2 weeks), presence or absence of each SDI domain item, and SDI worsening (change from baseline ≥1)
  - Proportion or frequency (number and percentage) of subjects
- Count of events such as hospitalizations
  - Incidence and events rates with 95% CI (see Section 7.2.4 below for detailed methodology)

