### 7.2.3. Population of Interest

The effectiveness analyses will be based on the “Evaluable” analysis population.

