### 9.6.2.3. Handling of Missing Data for Statistical Analysis

Element	Reporting Detail
General	
 
For endpoints not relying on multiple questionnaire items, missing values will not be imputed
 
Data will be analysed only for the time point at which they were collected.
 

SDI Domains	
 
If any item is missing, the total score should be missing. However, if the missing item has previously been score in previous visits, the worst observation can be carried forward for that item.
 
If the SDI is scored inconsistently (a decrease score at subsequent follow-up relative to previous visit has occurred) and the data are unable to be queried and/or corrected, the previous score (before the decrease) will be carried forward at the item level for the SLICC/Damage Index questions, this corresponds to worst observation carried forward (WOCF). These carried forward values at items level will then be used to calculate the total score which will be the value summarized and displayed for reporting.
 

S2K Score	
For the calculation of S2K score, all items will be taken from the completed SLEDAI 2000 CRF page; no imputation will be performed.
 
Scores for any S2K items will be used as observed. Subjects with at least one missing i.e. 'not done' value at baseline assessment will be excluded from the analysis of S2K total score.

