**9.11.3. Effectiveness Endpoints Tables**

Effectiveness Endpoints Tables			
Table No	Analysis Population	Title	Programming Note
SLICC/ACR Damage Index (SDI)			
11.000	Eligible	Summary of Baseline SLICC/ACR Damage Index (SDI)	
11.100	Evaluable	Change from Baseline in SLICC/ACR Damage Index (SDI) by Visit [Initial Exposure – ITT Strategy]	
Hospitalizations			
13.000	Eligible	Summary of Hospitalizations at Baseline by Study Cohort	
13.110	Evaluable	Summary of Hospitalizations Rate by Time Period [Initial Exposure – ITT Strategy]	
13.210	Evaluable	Summary of Hospitalizations Rate by Time Period [While On Initial Exposure Strategy]	
13.310	Evaluable	Summary of Hospitalizations Rate by Time Period [As-Exposed – Time Varying Strategy with 14 Weeks Risk Window]	
SLE Medications			
14.000	Eligible	Duration of Prior SLE Medications Not in Use at Baseline (Historical) by Study Cohort	
14.100	Eligible	Duration of Prior SLE Medications in Use at Baseline by Study Cohort	
14.200	Eligible	Frequency of Prior SLE Medications in Use at Baseline by Study Cohort	
14.300	Eligible	Frequency of Concomitant SLE Medications by Study Cohort	
Corticosteroids Use			
15.000	Eligible	Summary of Corticosteroids Usage at Baseline	
15.101	Evaluable	Change from Baseline in Average Corticosteroids Dose by Visit [Initial Exposure – ITT Strategy]	
15.201	Evaluable	Summary of Corticosteroids Usage by Visit [Initial Exposure – ITT Strategy]	

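### SAP 7.2.1 conditions the average corticosteroid dose on steroid use, while SAP 2.2 defines it for all subjects, and no rule counts a steroid-free window as 0 mg/day

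*SAP*

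**What the plan says.** SAP 2.2 sets endpoint 2b as "Comparison of mean change from baseline in six-month average daily corticosteroid dose (prednisone equivalent, mg/day) assessed over 5-year period", in adult SLE subjects exposed or unexposed to BENLYSTA. It has no restriction to steroid users.

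SAP 7.2.1 lists the variables to be analysed. It names a binary variable, "Use of concomitant corticosteroids (Yes or No"), and then opens a branch, "If concomitant corticosteroid use is" Yes. Two items stand under that branch: the three dose categories, and "Absolute and change from baseline of average corticosteroids dose (mg/day").

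SAP 7.2.2 summarises "absolute and change from baseline average corticosteroids dose (mg/day") by mean, SD, median, range and quartiles, for the endpoints listed in Table 3 and section 7.2.1. SAP 7.2.4 refers back to the same list. SAP 7.2.3 states: "The effectiveness analyses will be based on the" Evaluable population. Table 15.101 in SAP 9.11.3 is titled "Change from Baseline in Average Corticosteroids Dose by Visit", by initial exposure (ITT).

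On missing data, SAP 9.6.2.3 says: "For endpoints not relying on multiple questionnaire items, missing values will not be imputed". SAP 9.5.2 defines change as the follow-up value minus the baseline value. Protocol 6.2 has the average daily dose in prednisone equivalents recorded at each six-month point, with no condition on use.

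**The concern.** Steroid use is a named effectiveness measure in both documents, and tapering to zero is the largest dose reduction a patient can have. If the dose variable exists only when use is Yes, a patient who reaches zero and stays there stops contributing to the mean change. Whether a patient is in the mean then depends on the outcome being measured. The two groups are compared on subsets selected by that outcome, and the selection is stronger in whichever group stops steroids more often. A steroid-sparing difference could be hidden or distorted. A by-visit mean could even rebound as more patients reach zero. The result would also not be an estimate of endpoint 2b as SAP 2.2 defines it.

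**Working it through.** The documents give no mean dose, SD or stopping proportion for this endpoint, so there is no plan figure to reproduce. The check is first textual, then illustrative.

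**Text side by side**

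- Restricted to use = Yes: SAP 7.2.1.
- No restriction stated: SAP 2.2 (endpoint 2b), 7.2.2, 7.2.3, Table 15.101, Protocol 6.2.
- Sections 7.2.2 and 7.2.4 take their endpoints from the 7.2.1 list, so their silence does not cancel the condition. The Evaluable population settles who is in the set, but it does not give a non-user a dose value.
- A change value needs a dose at both baseline and follow-up (9.5.2). No text assigns 0 mg/day to non-use, and 9.6.2.3 does not impute. The SAP does write such rules elsewhere: absent or not-done items count as 0 in the clinical SLEDAI score (7.3.1.4), and SDI items are carried forward (9.6.2.3).

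**When a patient would drop out**

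The measure is a six-month average. A patient on 10 mg/day who stops a quarter, half or three quarters of the way through a window averages 2.5, 5.0 or 7.5 mg/day. If Yes is judged over that window, as a six-month average implies, the patient is still a user in it. The loss starts with the next window spent wholly off steroids.

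**Size, with assumed inputs**

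Let b be the mean baseline dose (the same in stoppers and continuers), c the mean change in continuing users, and q the share of baseline users now at 0 mg/day.

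- Users-only mean change = c
- All-patient mean change = (1 - q) × c + q × (-b)

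Take b = 10, c = -2.5, and q = 0.30 (BENLYSTA) versus 0.15 (comparison):

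- Users only: -2.5 in both groups, difference 0.
- All patients, BENLYSTA: 0.70 × (-2.5) + 0.30 × (-10) = -1.75 - 3.00 = -4.75.
- All patients, comparison: 0.85 × (-2.5) + 0.15 × (-10) = -2.125 - 1.50 = -3.625.
- Difference: -4.75 - (-3.625) = -1.125 mg/day.

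Range for the same 30% versus 15% split: with b from 7.5 to 10 and c from 0 to -2, the users-only difference stays 0 and the all-patient difference runs from -0.825 to -1.50 mg/day. Within one group, q from 10% to 40% makes the all-patient mean 0.55 to 4.00 mg/day more negative than the users-only mean.

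**Can the sign reverse?**

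Keep b = 10, the same stopping shares and comparison continuers at -2.5, and let BENLYSTA continuers change by x. Users only favours comparison when x > -2.5. All patients favours BENLYSTA when 0.70x - 3.00 < -3.625, that is x < -0.625/0.70 = -0.89.

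| x | Users-only difference | All-patient difference |
|---|---|---|
| -1.5 | +1.0 | -4.05 + 3.625 = -0.425 |
| -0.5 | +2.0 | -3.35 + 3.625 = +0.275 |

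So the sign reverses for x between -2.5 and about -0.89, and not outside that range.

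**The case against.** The strongest reply is that 7.2.1 is the only place with the condition, and that zeros may already be in the data. Protocol 6.2 records the average dose at every time point whether or not steroids are used. If sites enter 0, nothing is missing and the no-imputation rule is never reached. The eCRF is not in the documents and the mock shells are in a separate file, so the actual denominator of Table 15.101 cannot be seen. This stands as a limit on certainty. It does not remove the problem: 7.2.1 still excludes non-users whatever was entered, and without a rule, inclusion could depend on whether a site typed 0 or left a blank.

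A second reply is that stopping is measured anyway, through use Yes/No in 7.2.1 and the usage summary by visit in Table 15.201. That also stands: patients who stop are not lost from the steroid objective. But a proportion of users does not correct a mean change computed without them.

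Third, the stakes are modest. This is an 'other' endpoint with descriptive summaries and no formal testing (SAP 2.4, 5.7). Propensity weighting is confined to the primary objectives (SAP 7.3), so the steroid comparison is unadjusted for confounding in any case.

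Two stronger readings are tempting. A reader might infer that the endpoint is definitely computed only in patients on steroids on the visit day, so that every patient who tapers to zero disappears at once. The SAP does not say when Yes is judged, and a six-month average keeps a patient who stops part-way through the window. A reader might also infer that the sign of the group difference reverses whenever continuers fall less in the group with more stoppers. The table above shows that this holds only for some inputs.

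**Conclusion.** The point holds as a conflict between SAP 7.2.1 and SAP 2.2, with a missing zero-dose rule. Taken literally, 7.2.1 does not estimate endpoint 2b and introduces selection on a post-baseline outcome. The illustrative effect is about 0.8 to 1.5 mg/day in the group difference. That rests on assumed baseline doses of 7.5 to 10 mg/day, 30% versus 15% stopping, equal change among continuers in both groups, and equal baseline dose in stoppers and continuers. None of these figures is in the documents.

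Severity is moderate to minor. The documents do not support calling the steroid objective invalid, because use Yes/No is reported separately and recorded zeros may already exist. The primary safety objective is untouched.

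**What to change.** In SAP 7.2.1, move the absolute and change-from-baseline average dose out of the Yes branch so that it matches endpoint 2b in SAP 2.2. State that a six-month window with no corticosteroid use counts as 0 mg/day, at baseline and at follow-up, and that only unanswered steroid data are missing. Name all Evaluable subjects assessed at that visit as the denominator of Table 15.101. If a summary among continuing users is wanted, keep it and label it supplementary.

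The cost is a wording change and one derivation rule. New data should not be needed: Protocol 6.2 already has steroid start and stop dates and the average dose recorded at each time point, though the eCRF should be checked for how a visit without steroids is entered. The downside is a spike at 0 mg/day in the dose distribution, which the median already planned in SAP 7.2.2 handles when read beside the mean.
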